Document:

Study Protocol and Statistical Analysis Plan

Official Study Title:

Use of a Smartphone App Versus Motivational Interviewing to Increase Walking Distance and Weight Loss in Overweight/Obese Adults with Peripheral Artery Disease: Pilot Randomized Trial

NCT: NCT03694652

Document Date:

August 2022

Use of a Smartphone Application versus Motivational Interviewing to Increase Walking Distance and Weight Loss in Overweight/Obese Adults with Peripheral Artery Disease: A Pilot Randomized Trial

Materials and Methods

Participants

We conducted a two-arm, pilot randomized trial. Inclusion criteria were age 50 years or older, overweight/obese ($BMI \geq 27$), and symptomatic PAD – leg symptoms were captured by a validated survey and PAD was confirmed with the use of the ankle-brachial index (ABI) which is the ratio of the systolic blood pressure in the ankle to that in the arm. Our cut-point for the ABI was <0.9 .

Individuals were excluded if they demonstrated at least one of the following conditions: intolerance to fruits, vegetables, fiber, and/or a low-fat diet, restricted water intake, pregnant, prior major ischemia or critical leg ischemia, use of 24-hour supplemental oxygen, heart attack within the last 3 months, inability to walk for exercise, or currently walking at least 3 days per week for at least 30 minutes each day. The University of Kansas Medical Center Institutional Review Board (KUMC IRB) approved this study and participants gave informed consent. The clinical trial registration for this study is NCT03694652.

Recruitment

We recruited study participants using a variety of modalities which included both the University of Kansas hospital system as well as unaffiliated health centers and community-based clinics.

Smartphone App vs. MI for Management of Peripheral Artery Disease

Area clinicians and administrators voluntarily distributed flyers and mailings to eligible patients. We obtained KUMC IRB approval—as well as permission from participating hospitals and clinics--prior to each phase of the recruitment process.

Interventions

Motivational Interviewing (MI)

Participants randomized to MI participated in an initial one-hour, face-to-face session. Following the initial visit, we conducted four, 20-minute telephone calls; one call every two weeks for one month followed by two monthly phone calls.

Author KR provided MI counselor training through a series of workshops. The counselor was a medical school graduate and a student in the master's in public health program at KU School of Medicine-Wichita who was also applying for residency in primary care. Although the counselor had no experience in MI prior to this trial, author KR has trained multiple research staff in the delivery of MI. There were standardized patients and ongoing review of sessions through direct observation. The counselor's goals were to elicit and reinforce change talk about increasing walking behavior and healthy dietary habits.

During each counseling session, the counselor assessed participants' willingness to walk for exercise using the Patient-centered Assessment and Counseling for Exercise survey (PACE), which assesses readiness to exercise.[20, 21] Following a discussion of their current PACE score, the counselor queried patients about the importance of exercising and their current

Smartphone App vs. MI for Management of Peripheral Artery Disease

motivation to increase walking behavior. The counselor concluded each session by offering patients the option to set a walking goal for the next two weeks.

The counselor followed a similar process with respect to the nutritional portion of the interview. She guided patients to choose one of six nutritional options to work on in the following two weeks: (1) reducing sodium, (2) increasing fruits, (3) increasing vegetables, (4) decreasing sugary drinks, (5) increasing whole grains, or (6) mindful eating. Similar to the exercise therapy, the counselor discussed the importance of change, patients' confidence levels, and individual values. After patients established exercise and nutritional goals, counselors would arrange for subsequent follow-up sessions at two-week intervals.

Smartphone Application

Development

We created the PAD Mobile App with support from the Center for Excellence in Health Communication to Underserved Populations at the University of Kansas School of Journalism and Mass Communication. Author MG supervised the design, operational functionality, and development of the App. We employed iterative feedback from experts and research team members to design the user interface, content, and functionality.

The App was designed for use with Android OS smartphones—patients without this type of phone received it as part of the study. We tailored nutritional content for clarity and lower health literacy levels. We designed the mobile app to allow users to input walking plans, track walking intervals, and record episodic pain. We designed in-app notifications to encourage patient use as well as diet and exercise management.

Smartphone App vs. MI for Management of Peripheral Artery Disease

The App was completely automated and adaptive to patient use. The study team was available to troubleshoot and answer questions as needed. Safeguards permitted recovery of previously saved data in the event of accidental malfunction. Participant data was encrypted and saved locally to the phone. Once initialized, the App sent secure, de-personalized data to an online backup server via the internet.

Table 1. Behavior Change Techniques – Nutrition and Physical Activity

Technique	MI	App
1.1 Goal Setting (behavior): agreed on weekly walking goals	✓	✓
1.2 Problem solving: identifying triggers to eating unhealthy foods or avoiding walking for exercise	✓	✓
1.4 Action planning: setting aside time to exercise and planning meals in advance	✓	✓
1.6 Discrepancy between current behavior and goal: recorded walking goals or self-reported dietary goals were not met		✓

Table 1. Behavior Change Techniques – Nutrition and Physical Activity (cont'd)

Technique	MI	App
3.1 Social Support (unspecified): participants received recommendations on the value for having a buddy to walk with	✓	✓
4.1 Instruction on Walking Therapy to Improve Walking Distance	✓	✓
4.3 Re-attribution: if a participant attributed their desire for food to boredom, we provided guidance on mindfulness eating		✓

Smartphone App vs. MI for Management of Peripheral Artery Disease

5.1 Information about health consequences: participants were provided information about the potential for disease progression in the absence of a walking intervention	✓	✓
5.4 Monitoring of emotional consequences: participants were queried about satisfaction with their weekly dietary and walking goals		✓
8.2 Behavior substitution: participants were provided with guidance on substituting unhealthy dietary choices with healthy dietary choices		✓
9.1 Credible source: participants viewed videos in which the Principal Investigator, who is board certified in internal and vascular medicine, shared the importance of walking for exercise for persons with PAD		✓
9.2 Pros and cons: participants were queried regarding the pros and cons of eating a healthy diet as well as walking for exercise	✓	✓
10.4 Social reward: participants were congratulated for achieving their weekly goals		✓

Table 1. Behavior Change Techniques – Nutrition and Physical Activity (cont'd)

Technique	MI	App
13.2 Framing/reframing: participants were provided with cognitive structuring to think of tasks to reduce sedentary behavior	✓	✓
15.1 Verbal persuasion about capability: participants were told they can walk for exercise despite leg discomfort	✓	✓

Michie et al, 2013

Implementation

We developed the PAD Mobile App specifically for this pilot study based on the PACE and MI principles described above. The PAD Mobile App had two distinct components: a nutritional component and a walking component. Similar to the MI group, the nutritional component of the mobile App contains six modules, with each of the six topics designed to be completed over a two-week time period. We designed each module to reflect nutritional issues specific to PAD patients. Of these modules, patients were permitted to choose the order of completion—yet, this completion was self-initiated. The App employed identical measures for assessing patients' perceptions of the importance of change, confidence levels, and individual values. The App utilized the PACE format to set exercise goals, and self-assessment to set nutritional goals over a 12-week period. Similar to the MI group, nutritional modules were further divided into six, two-week cycles.

On the first day of the study, patients installed the App, and it prompted them to enter their demographic, health, and identity information. The App then presented patients with six possible nutritional changes that they could choose to address during the first two-week cycle (Figure 1). Once participants chose one of the six dietary modifications, they were prompted to perform a self-assessment; the App would then adjust goals according to patients' responses.

We made explicit efforts to ensure that patients would not have trouble installing, using, or interacting with the application. Several safeguards were installed to provide patients with continuous support and resources. The App provided extensive exercise tracking (Figure 1) as well as a comprehensive reporting menu with information about patient progress (Figure 1).

Smartphone App vs. MI for Management of Peripheral Artery Disease

Automatic reminders prompted participants to engage with the App and to select their next PAD intervention cycle at two-week intervals.

Measures

Ankle-Brachial Index (ABI)

The ABI was used to define the presence or absence of PAD. During this assessment, a participant rested for 5 minutes and a 5 MHz hand-held Doppler with an attached stethoscope was used to measure systolic blood pressures in both brachial arteries and in both ankles (i.e., the dorsalis pedis and posterior tibial arteries).[22]

Medical History

The PI and colleagues developed the Lifestyle and Clinical Survey (LCS) to obtain patients' medical history—including smoking status—sociodemographic, and comorbidity data. It has a summary k-statistic for reliability of 0.81 (95% confidence interval [CI] 0.78, 0.84) and a summary k-statistic for validity of 0.58 (95% CI 0.52, 0.64).[23]

Stage of Readiness to Engage in Exercise

The Patient-Centered Assessment and Counseling for Exercise (PACE) score was used to identify a participant's readiness for exercise. To obtain a PACE score, a participant chose one of eight graded statements that best described his/her current level of and interest in physical exercise [24, 25] We assessed a participant's PACE score at baseline and 6 weeks; we employed these assessments to tailor each intervention to each patient's respective stage of readiness.

Outcomes

The primary outcome was the three-month change in walking distance, as measured by the 6-minute walk test (6MWT). The 6MWT provides information on a patients' ability to walk in the community. The test is conducted by placing two cones 100 feet apart in a marked hallway and instructing patients to walk as many laps around the cones as possible. Patients were permitted to stop walking during the test; however, time was recorded during the rest period. We recorded time and distance to onset of leg discomfort and total feet walked. In a prior study involving 64 patients with PAD, the reliability coefficient for distance during 6-minute walk tests performed one week apart was 0.94 with a coefficient of variation of 11.7%.[26]

Secondary outcomes included weight loss, quality of life, exercise behaviors, and dietary habits. For weight loss, we used a standardized scale to measure body weight. For health-related quality of life, we used the validated Vascular Quality of Life Questionnaire (VascuQol Score).[27] The intraclass (reliability) coefficient for the VascuQol was 0.94 (CI > 90%), and Cronbach α ranged between .7 and .9, indicating good internal consistency within the five domains. The VascuQol total score has a correlation with the Fontaine classification of disease severity [28] of $r = -0.79$ ($P < .001$) and with treadmill walking distances of $r = 0.36$ ($P < .05$). For self-reported physical activity, we used the validated Stanford Patient Education Research Center Exercise Behavior Survey.[29, 30] The Exercise Behavior Survey retest reliability scores between 0.56-0.72. We employed the Fat-Related Diet Habits Questionnaire[31] to assess basic consumption as well as healthier choices, such as substitution of low-calorie or low-fat food alternatives. We modified the survey to a 3.9 reading level. The Fat-Related Diet Habits Questionnaire has high test-retest and internal consistency reliabilities and correlations with percent of calories from fat ranging from 0.34 to 0.57 ($P < .01$). The correlation of the sum of the five scales with percent of

Smartphone App vs. MI for Management of Peripheral Artery Disease

calories from fat is 0.68 ($P < .001$) and, in multiple regression models, the multiple R² using all factors to predict percent of calories from fat was 0.47. All outcomes were measured at baseline and 3 months.

Study Flow

Screening

We pre-screened potential participants via phone. The pre-screen assessment captured (1) physical activity readiness (Physical Activity Readiness Questionnaire [PAR-Q]) - the PAR-Q was used to identify conditions which would preclude participation in the study[32], and (2) leg symptoms (San Diego Claudication Questionnaire).[33] Based on eligibility criteria, we scheduled candidates for an in-person visit.

Baseline In-person Visit and Randomization

After obtaining informed consent, a blinded assessor measured individuals' ABI, weight and height. We referred eligible candidates to graded submaximal treadmill testing, as per American College of Cardiology guidelines.

Upon completion of treadmill testing and without evidence of coronary ischemia, participants completed questionnaires to assess quality of life, exercise behaviors, and dietary habits. We then randomly assigned participants to the App or MI. We used a random number generator to blindly assign patients to one of the two groups.

Analysis Plan

We used Wilcoxon rank-sum test to analyze the primary outcome of change in 6-minute walking distance at three months within the MI and App groups, and to compare the changes between the groups with adjustment for baseline (difference in difference). We used this same method for other outcomes. For comparing participants' baseline characteristics between the MI and App groups, we used Wilcoxon test for continuous measurements and Fisher's test for dichotomous measurements. We use R version 4.03 (R Foundation for Statistical Computing) for all data analyses.

Thirteen participants per group were required to provide 80% power at a0.05 error level and to detect a difference between the two groups of 50 meters walking distance change.

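### Does naming only a rank-sum test, in a trial sized on 50 m, leave a non-significant result unreadable?

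*Combined protocol and SAP*

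**What the plan says.** The Analysis Plan opens with the primary method: "We used Wilcoxon rank-sum test to analyze the primary outcome of change in 6-minute walking distance at three months". That clause goes on to the within-arm changes. The between-arm part follows in the same sentence, where the test is also used "to compare the changes between the groups with adjustment for baseline (difference in difference"). The other outcomes are handled in the same way.

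The last paragraph of the Analysis Plan gives the sizing: "Thirteen participants per group were required to provide 80% power at a0.05 error level and to detect a difference", the target being to "detect a difference between the two groups of 50 meters walking distance change". It states no SD of change, sidedness or sizing test.

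Under Outcomes, distance is recorded in feet: "We recorded time and distance to onset of leg discomfort and total feet walked". The only variability figure for the walk test is also there, from an earlier study: "the reliability coefficient for distance during 6-minute walk tests performed one week apart was 0.94 with a coefficient of variation of 11.7" percent. The Participants section describes the design: "We conducted a two-arm, pilot randomized trial".

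No point estimate or confidence interval is named for any trial outcome. The confidence intervals that do appear, under Measures and Outcomes, describe the reliability or validity of instruments.

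**The concern.** The sizing target is a distance in metres, whereas a rank-sum p-value is a statement about zero. A p-value above 0.05 can arise when the data rule out 50 m and also when they leave it open, and the p-value alone does not separate the two. For a pilot this looks costly, because the size of the difference, its precision and the SD of change are what a later trial would be planned from.

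Two smaller points add to the impression. The phrase about adjustment for baseline could be read as a covariate step, which a rank-sum test cannot take. Distance is recorded in feet while the target is in metres.

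**Working it through.** **Inputs.** From the last paragraph of the Analysis Plan: 13 per group, 80% power, alpha 0.05, difference 50 m. Not given: SD of change, sidedness, sizing test.

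**The plan's own figure.** It cannot be computed forward without an SD, so solve for the SD that returns 13.

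- Normal approximation, two-sided: n = 2(1.960 + 0.842)² × SD² / 50². Since 2(2.802)² = 15.70, SD = 50 × √(13 / 15.70) = 45.5 m.
- Noncentral t with 24 df, two-sided: 43.7 m.
- Exact rank-sum with normal data, by simulation, two-sided: 41.5 m.
- One-sided: about 47.5 m (rank-sum), 49.8 m (t), 51.3 m (normal).

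Thirteen per group fits an SD of roughly 41 to 51 m, depending on the method. It is neither confirmed nor refuted. The quoted coefficient of variation does not settle the matter: it is for tests one week apart, not three months, and no mean distance is given.

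**Precision that the design implies.** For 13 v 13 the exact two-sided rank-sum test has critical U = 45 (actual alpha 0.044). Inverting it gives an interval from the 46th smallest to the 46th largest of the 13 × 13 = 169 pairwise differences. As a rough check from the t formula at SD 41.5 m: 2.064 × 41.5 × √(2/13) = 2.064 × 16.28 = 33.6 m. Simulating the rank-sum interval with normal data gives:

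| SD of change (m) | Mean half-width (m) | True 0: non-significant | of which include +50 m | True 25 m: non-significant | of which include +50 m |
|---|---|---|---|---|---|
| 41.5 | 35 | 96% | 19% | 72% | 61% |
| 43.7 | 37 | 96% | 23% | 74% | 66% |
| 47.8 | 40 | 96% | 31% | 78% | 71% |
| 60 (assumed) | 51 | 96% | 52% | 84% | 82% |

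The sizing target has no direction, so -50 m counts too. At a true difference of 0, the share of non-significant intervals that include either value is about 37% at SD 41.5 m and about 61% at SD 47.8 m, roughly double the +50 m column.

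The p-value does not stand in for the interval. At SD 41.5 m and p between 0.29 and 0.34 in the App's favour, about 57% (true 0) to 68% (true 25 m) of intervals include 50 m, and the rest exclude it.

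**Is anything in the plan wrong as a result?** Set the statements side by side.

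- *Test and outcome.* The outcome is three-month change; the between-arm test compares changes. These agree, and the test is valid for that comparison.
- *Test and sizing target.* The target is a between-arm difference in change, which is the contrast tested. The plan attaches no equivalence, futility or go/no-go reading to 50 m and does not call it a minimal important difference.
- *Baseline adjustment.* The plan glosses the phrase itself as a difference in difference and speaks of comparing changes. The natural reading is change scores, which need no further covariate. With assumed change-baseline correlations of -0.3 to -0.5, a second adjustment would alter significance in 10% to 18% of trials at a true 25 m, but the documents support neither those correlations nor that reading.
- *Units.* 50 m / 0.3048 = 164 ft, which is a conversion and not a conflict.

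**The case for a change.** The strongest argument for a change is that the repair costs almost nothing. The Hodges-Lehmann difference with its test-inverted 95% interval needs no extra patients and leaves the p-value on change scores as it is. Naming the estimator in advance would also remove a choice between a mean difference, a difference of medians and a Hodges-Lehmann shift. The pilot status strengthens this, since precision matters more than a verdict on significance, and the table shows that the p-value cannot supply it.

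The argument stands as advice on reporting: the interval is informative, and a results section without it would be weaker. It does not stand as a correction. No stated rule or number is shown to be wrong, and nothing in the text stops the analyst from reporting an estimate in metres with its interval and the SD of change per arm. The question of whether 50 m is excluded is a good one, but it comes from the reader; the plan does not set it. The document is also dated August 2022 and written in the past tense, so an estimator labelled primary now could be a choice made after the data. Whether a rank-sum test suits the within-arm changes, which are paired, is a separate question and does not bear on this one.

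**Conclusion.** No change to the plan is needed. The missing estimate and interval are a gap in a two-paragraph analysis section, one that an analyst fills from the test already named. The between-arm comparison is valid as written and matches the quantity used for sizing.

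The information at stake is real. Half-widths of about 35 to 40 m against a 50 m target mean that many non-significant results would leave 50 m open: at a true difference of 0, about 37% to 61% when both directions are counted, for SDs of 41.5 to 47.8 m. These figures assume normal changes, 13 analysed per arm, and an SD inferred from the plan's own power statement. A larger SD would widen the interval, to about 51 m either side at an assumed 60 m. The conclusion does not depend on the SD, because it concerns what the plan permits and not how precise the trial turns out to be.

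### The plan names the Wilcoxon rank-sum test, an independent-samples test, for paired within-arm changes; run that way, the within-arm tests are conservative and lose power

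*Combined protocol and SAP*

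**What the plan says.** The first sentence of the Analysis Plan assigns one test to two tasks. It uses the "Wilcoxon rank-sum test to analyze the primary outcome of change in 6-minute walking distance at three months within the MI and App groups", and the same test for comparing the changes between the arms. The next sentence widens the scope: "We used this same method for other outcomes". The other outcomes, listed under Outcomes, are weight, quality of life, exercise behaviors and dietary habits.

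On timing, Outcomes states: "All outcomes were measured at baseline and 3 months".

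The only other mention of a Wilcoxon procedure concerns baseline characteristics of the two arms, where "we used Wilcoxon test for continuous measurements". That is a between-arm use and does not say which variant is meant. Neither a signed-rank test nor any other paired test is mentioned.

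**The concern.** Within one arm there is a single group of people, each measured twice. The rank-sum test needs two independent groups. It can be run within an arm only by setting the baseline values against the 3-month values as if they came from different people, which discards the pairing.

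With positive correlation between a patient's two measurements, this makes the test conservative. It rejects too rarely when nothing has changed and misses real change when something has. At stake are the within-arm p-values for the primary outcome and, through the extension sentence, for every secondary outcome. A real change could be reported as non-significant. Even if the correct test was run, a reader cannot tell that from the text and cannot reproduce the within-arm results.

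**Working it through.** **The plan's own figure.** The plan gives 13 per group, 80% power and an error level of 0.05 "to detect a difference between the two groups of 50 meters walking distance change". It states neither an SD nor whether the test is one- or two-sided, so 13 cannot be confirmed; it can only be solved backwards for the SD of change.

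- Normal approximation: SD = 50 / [(z for alpha + z for power) × sqrt(2/13)], with sqrt(2/13) = 0.392.
- Two-sided: 50 / [(1.960 + 0.842) × 0.392] = 45.5 m; with the t-test, 43.65 m.
- One-sided: 50 / [(1.645 + 0.842) × 0.392] = 51.3 m; with the t-test, 49.8 m.

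The illustration uses 43.6 m (the two-sided t-test value) and 50.5 m, a round figure between the two one-sided values.

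**Correlation.** The plan gives no baseline to 3-month correlation for any outcome. It gives short-term reliabilities: 0.94 for the 6-minute walk test repeated after one week, and for physical activity "The Exercise Behavior Survey retest reliability scores between 0.56-0.72". These support a positive correlation but are not three-month values, so rho is varied and 0.94 is treated as an upper end.

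**Standard-error factor (needs no SD).** With equal SD s at both times and n pairs:

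- Paired variance of the mean change: 2s²(1 − rho)/n.
- Variance if the values are treated as independent: 2s²/n.
- Ratio of standard errors: 1/sqrt(1 − rho). At rho 0.5 this is 1/sqrt(0.5) = 1.41; at 0.8 it is 1/sqrt(0.2) = 2.24.

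**Simulation.** 13 pairs, bivariate normal, 40,000 trials per cell, SD at each visit = SD of change / sqrt(2(1 − rho)). Exact two-sided tests at 0.05: signed-rank critical value 17 (size 4.8%), rank-sum U critical value 45 (size 4.4%). The within-arm gains of 50 m and 25 m are assumptions; the plan's 50 m is a between-group difference. Power is shown for SD of change 43.6 m / 50.5 m.

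| Test and rho | SE factor | Type I error | Power, 50 m gain | Power, 25 m gain |
|---|---|---|---|---|
| Signed-rank, any rho | 1 | 4.6% to 5.0% | 96% / 89% | 46% / 36% |
| Rank-sum, 0.3 | 1.20 | 2.0% | not run | not run |
| Rank-sum, 0.5 | 1.41 | 0.8% | 83% / 68% | 20% / 14% |
| Rank-sum, 0.56 | 1.51 | 0.6% | 78% / 62% | not run |
| Rank-sum, 0.72 | 1.89 | 0.15% | 54% / 37% | not run |
| Rank-sum, 0.8 | 2.24 | 0.04% | 35% / 21% | 3% / 2% |
| Rank-sum, 0.94 | 4.08 | below 0.01% | 2% / 1% | not run |

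**Sensitivity.** A separate simulation of 20,000 trials per cell with SD of change 43.5 m gave the same pattern: rank-sum power for 50 m of 83%, 35% and 2% at rho 0.5, 0.8 and 0.94. At rho 0 the two tests were about equal (97% rank-sum, 96% signed-rank). Fixing the SD at each visit at 80 to 120 m instead, with rho from 0.5 to 0.94, gave rank-sum power for 50 m of 2% to 25%, against 26% to 100% for signed-rank.

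**The case against.** The best reply is that this is a naming slip. The sentence applies the test to change, and Outcomes defines the primary outcome as a three-month change. Change within one arm is a single column of numbers, on which a two-sample test cannot be run. To obtain an unpaired analysis one must go back to raw baseline and 3-month values, which the text does not describe. A single test name covering two analyses, and the looser name used a sentence later, point the same way. This reading is plausible and may be right. It does not remove the defect: rank-sum is the specific name of the unpaired test, and nothing in the document settles which test was run.

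Second, the consequence is limited. The error is conservative, the sample size rests on the between-arm difference, and within-arm change is weak evidence anyway because no untreated arm separates treatment from time or practice. All of this stands and limits the weight of the point. It does not make the point trivial, since within-arm change comes first in the primary-outcome sentence.

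Third, the power figures depend on an assumed SD, correlation and gain, and the 0.56 to 0.72 range belongs to a different instrument from the walk test. That is correct. The standard-error factor does not depend on the SD or the gain, but it still depends on rho.

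Fourth, questionnaire scores will probably contain ties and zero changes, which the normal simulation does not represent. That also stands, and the corrected text should say how they are handled.

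**Conclusion.** The concern holds: the test named for within-arm change does not fit paired data, for the primary outcome and, by extension, all others. That rests on the text alone and is firm.

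The consequence is conditional on the unpaired test having been run. In that case any positive correlation makes the within-arm tests conservative, so false claims of improvement occur in fewer than 5% of null cases (not in none), and real changes are missed more often. For a 50 m gain the loss is moderate at rho 0.5. It is already large at 0.72, where power falls by 42 points (96% to 54%) or 52 points (89% to 37%), and greater at 0.8. For a 25 m gain, power is more than halved even at rho 0.5. These sizes assume 13 patients per arm, normal data, a back-solved SD of change and an assumed correlation.

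The between-arm rank-sum comparison of changes uses independent patients and is not affected by the pairing problem. Whether it delivers the stated adjustment for baseline is a separate question, not judged here. The point should be fixed, but it does not threaten the randomised comparison.

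**What to change.** 1. Check in the R code which test was run within each arm.
2. Correct the Analysis Plan, for example: *Within each arm, each patient's 3-month minus baseline difference was tested with the Wilcoxon signed-rank test, for the primary and all other outcomes.* Add how ties and zero changes were handled, which matters mainly for the questionnaire scores.
3. Confine the rank-sum wording to between-arm comparisons of change.
4. If any within-arm p-value came from the unpaired test, recompute it. If the signed-rank test was already used, only the wording changes.

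Reporting the Hodges-Lehmann median change with its 95% confidence interval would be good practice, but is optional.

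The cost is a small edit to the Analysis Plan and a code check; at most, one argument of the test call changes and the within-arm tests are rerun. No new patients or data are needed.

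### Is the 80% power claimed for 13 participants per group wrong, given that no SD of change is stated?

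*Combined protocol and SAP*

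**What the plan says.** The sample-size justification is the last sentence of the Analysis Plan: "Thirteen participants per group were required to provide 80% power at a0.05 error level". The effect sought is a between-arm gap of 50 m in how far the walk-test result changes. The sentence gives no SD, does not say whether the error level is one- or two-sided, names no test for the sizing, and does not say whether 13 counts enrolled or evaluable participants.

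The same section names the analysis: "We used Wilcoxon rank-sum test to analyze the primary outcome of change in 6-minute walking distance at three months", with the groups also compared after adjustment for baseline.

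The only figure on the variability of the walk test is under Outcomes, where a prior study of 64 patients with PAD is cited: "the reliability coefficient for distance during 6-minute walk tests performed one week apart was 0.94 with a coefficient of variation of 11.7" per cent. It appears there as evidence that the test is reliable. Neither the mean distance in that study nor the definition of the CV is given, and the sample-size sentence does not refer to it.

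**The concern.** A power statement for a difference in means cannot be checked without an SD. Here the SD has to be inferred, and the ceiling it implies, about 44 m, leaves little slack. Three things could push the true power below 80%:

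- **Retest noise.** On one reading of the 11.7% CV, measurement error alone could use up the whole 44 m, before any variation between people in their three-month response.
- **The planned test.** If 13 came from a t-test formula, the rank-sum test would have somewhat less power with normal data.
- **Drop-out.** A change score needs both walk tests, and no allowance for loss is stated.

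The stake is interpretation. The 80% is the trial's only formal planning claim. If it is overstated, a non-significant comparison of the App with motivational interviewing could be taken as better evidence against a 50 m difference than it is.

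**Working it through.** **Inputs.** From the Analysis Plan: n = 13 per group, difference 50 m, error level 0.05, power 80%. From Outcomes: CV 11.7%, reliability 0.94. Not in the document: SD of change, sidedness, sizing test, drop-out, mean walking distance.

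**1. Reproducing the 13.** This cannot be done forwards without an SD, so solve for the SD.

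- Normal approximation, two-sided: SD = 50 / [(1.960 + 0.842) × √(2/13)] = 50 / 1.099 = 45.5 m.
- Noncentral t, two-sided: the standardised difference giving 80% power at 13 per group is 1.145, so SD = 50 / 1.145, or 43.65 m without rounding.
- Noncentral t, one-sided: 49.8 m.
- Exact rank-sum test, two-sided, simulated with normal data (40,000 runs): power 83%, 81% and 79% at SD 40, 41 and 42 m, so the ceiling is about 41.5 m.

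Each of these SDs is consistent with 13 per group. No arithmetic error is visible; one input is unreported.

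**2. Power if the SD is larger** (two-sided t-test, 13 per group): 69% at 50 m, 53% at 60 m, 42% at 70 m. The document does not say which SD applies.

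**3. The retest CV.** The mean distance is an assumption, so a range is shown. Reading A takes the CV as within-person SD over the mean, so SD of change = √2 × 0.117 × mean. Reading B takes it as SD of the difference over the mean, so SD of change = 0.117 × mean.

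| Assumed mean (m) | A: SD (m) | A: power | B: SD (m) | B: power |
|---|---|---|---|---|
| 250 | 41 | 84% | 29 | 99% |
| 300 | 50 | 69% | 35 | 94% |
| 350 | 58 | 56% | 41 | 85% |
| 400 | 66 | 46% | 47 | 74% |

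The 43.65 m ceiling is reached at a mean of 43.65 / (√2 × 0.117) = 264 m under A and 43.65 / 0.117 = 373 m under B. Below those means the CV fits the ceiling.

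The reliability of 0.94 does not settle which reading is meant. If it is an intraclass correlation from the same data, the SD across patients would be 0.117 / √0.06 = 48% of the mean under A and 0.117 / (√2 × √0.06) = 34% under B.

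**4. The rank test.** At an SD of 43.65 m the exact rank-sum test has about 76% power with 13 per group; at 44 m it needs 14 for 80%. That shortfall arises only if the SD was set at the t-test ceiling. If the sizing used the rank test, or an SD of 41 m or less, 13 is enough.

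**5. Drop-out.** If 13 means enrolled, 11 or 10 evaluable per group at an SD of 43.65 m gives t-test power of 72% or 68%. If 13 means evaluable, enrolment at an assumed loss of 10%, 15% or 20% would be 13/0.90, 13/0.85 or 13/0.80, which round up to 15, 16 or 17. The wording allows either meaning.

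**6. Baseline adjustment.** Taking 0.94 as the correlation between visits (an assumption), adjustment multiplies the SD of change by √[(1 + 0.94)/2] = 0.985, a cut of about 1.5%. It neither rescues nor undermines the figure.

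**The case for a change.** The best case for a change is that the document itself makes a formal power claim, so pilot status does not excuse leaving out the one number needed to check it. Retest error over one week excludes differences between people in three-month response to a behavioural programme, so either reading of the CV more likely understates the SD than overstates it. The expected 95% confidence interval for the group difference has a half-width of 2.064 × 43.65 × √(2/13) = 35 m at the ceiling and 49 m at an SD of 60 m, the latter almost the whole target difference. The remedy would be one reworded paragraph and no extra participants.

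Much of this stands. The omission is real, the SD is plausibly larger than 44 m, and a non-significant result in a trial of this size would not show that the two programmes are alike.

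What does not stand is the step from an unverifiable figure to a wrong one. Every route to a lower power needs something the document does not supply: a mean distance, a CV definition, the two-sided t-test as sizing method, or 13 as an enrolment count. Power near one half appears only in some rows of the less favourable CV reading. The document also claims no equivalence or similarity between the arms that would rest on the 80%.

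**Conclusion.** No change to the plan follows. The sample-size sentence lacks its SD, sidedness, sizing test and drop-out assumption, and so cannot be verified. It implies an SD of change of at most about 44 m (two-sided t-test), about 41.5 m (rank-sum test) or about 50 m (one-sided t-test), and 13 per group is arithmetically sound at those values. Whether they suit this population cannot be decided from the document. The apparent clash with the 11.7% CV depends on a mean distance above 264 m or 373 m according to the reading, and neither the mean nor the reading is stated.

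This is a gap in reporting. Supplying the SD and its source would be good practice, but the group comparison does not use the planning SD, so the test, the analysed data and the result would be the same. The document is also written in the past tense, as an account of a pilot already conducted; the precision achieved will be judged from the observed spread of the changes and the number of participants with both walk tests. The power figures here assume normally distributed changes with equal spread in the two arms.
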